5.4 Laboratory Evaluations

5.4.1 Clinical and Research Laboratory Evaluations and Specimen Collection

Pediatric and adult subjects aged ≥ 3 years with upcoming clinical endoscopy will be asked to allow the investigators access to the FFPE specimens obtained as part of SOC, as well as given the option to donate two additional biopsies for this research. Subjects will be asked to provide these specimens at each SOC endoscopy for the life of the study. The research biopsies will be used for RNA and/or protein analysis. The immunological and histological analyses will generally be performed on the tissue normally taken for routine pathological evaluation.

It is important to point out that all subjects will have archived FFPE specimens available. So, despite some subjects declining the additional research biopsies, we will still be in a position to subsequently analyze specific genes in follow up validation studies and/or to test specific hypotheses that may later develop such as those about particular patient phenotypes.

5.5 Substudies

For a subset of 30 subjects, the histology scoring tool will be tested for inter- and intra-observer reliability at baseline and end of treatment for acceptable variability.

Exploratory

Study subjects will be the same as those recruited in Aim 1 but the study will be limited to analysis of 20 samples from each subject group with active diseases and no therapy, as well as respective control samples (tissue from subjects that have normal histology and no history of any GI disorder). This number was selected based on our prior work, where we were clearly able to detect substantial and significant differences between EoE and EG vs. their respective controls with even fewer patients³⁴.

Additionally, financial resources limit performance of gene expression profiles on all patients enrolled in this study. It is important to point out that all patients will have biopsy samples collected for RNA analysis as well as archived FFPE specimens available. So, we will be in a position to subsequently analyze specific genes in follow up validation studies and/or to test specific hypotheses that may later develop such as those about particular patient phenotypes. If the subject subsequently undergoes successful therapy, we will also assess his/her second biopsy for changes in the mRNA transcript profile following SOC treatment. EoE, EG, and EC as well as resolution of EoE, EG, and EC will be defined as in Aim 1. Patients who consent to the procurement of an extra biopsy sample, will have 2 research biopsies collected in RNALater and shipped to the [name] lab. Since EG and EC are

August 8, 2016

not yet well characterized, and based on our preliminary analysis that gastric tissue has minimal overlap with the EoE transcriptome, we will initially focus on taking a genome wide approach using commercial high density expression chips, as reported^{34, 36}. As a control, we will analyze gastric and colonic biopsy tissue from subjects who have no histological abnormalities and no history of prior gastrointestinal disease, similar to the approach we have taken for the esophagus^{34, 36}.

Creation of Bio repository

Exploratory Objective- To isolate and study some of the proteins, RNA, and DNA (the material contained in genes) from the blood/saliva/stool such as the level of eosinophil attraction proteins (eotaxins) and eosinophil growth factors (such as interleukin 5). We will bank the DNA for future studies including genome wide association analyses, candidate gene analyses, microbiome analysis and sequencing. Results will be deposited into dbGAP if required by NIH

5.6 Mechanistic sub-study

Role of the Intestinal Microbiome in Eosinophilic Esophagitis (EoE), Eosinophilic Gastritis (EG), and Eosinophilic Colitis (EC)

For a subset of 144 to 150 subjects we will conduct a prospective, observational study that will quantitatively characterize the microbiome of pediatric and adult subjects with Eosinophilic Esophagitis (EoE), Eosinophilic Gastritis (EG), and Eosinophilic Colitis (EC) by characterizing alpha and beta diversity at the taxonomic level within and between these groups.

5.7 Background Information

5.7.1 Description of the Study

This protocol aims to study patients with Eosinophilic Esophagitis (EoE), Eosinophilic Gastritis (EG), and Eosinophilic Colitis (EC) and compare them with normal controls. We hypothesize that the GI tissue, serum and stool from EoE, EG, and EC subjects will have a distinct dysbiotic microbial pattern as compared with the GI tissue, serum and stool from healthy control subjects. We further hypothesize that EoE, EG, and EC will have both similar and unique patterns of dysbiosis from one another.

5.7.2 Summary of Epidemiological Data

Substantial research has provided evidence that the recent emergence of numerous chronic inflammatory autoimmune and allergic disorders can be explained by the hygiene hypothesis, which postulates that exposure to microorganisms directs immune development and response, particularly during early life³⁷⁻⁴⁰. Experimental and epidemiological studies have tested this hypothesis by exploring the role of endogenous commensal flora in the GI tract since dysbiosis of commensal organisms has been linked to non-infectious pathological immune responses in mice and humans⁴¹. For example, elegant studies of gnotobiotic and specific pathogen-free mice have found significant defects in the development of gut-associated immune tissues in germ-free mice [6,7]. These mice also develop significant autoimmunity upon pathogenic challenge. Additionally, dietary consumption of low-level antibiotics used for the treatment of infections leads to microbial patterns associated with allergy predisposition⁴⁰. These studies clearly suggest a complex relationship between endogenous bacterial populations and the patterning of immune regulation/dysregulation with regard to allergic and inflammatory diseases.

In the context of EoE and exposures, CEGIR Investigator [name] has recently demonstrated that early-life antibiotic exposures increase EoE risk by 6 fold⁴⁴. Additionally, Dellon et al. have

shown that gastric *Helicobacter pylori* infection is inversely related to EoE risk, providing further support for the complex interactions of microorganism exposure, microbiome population, and esophageal and gastric immune responses⁴⁵. A collaboration of several CEGIR Investigators has recently shown that dizygotic twins have a 10-fold higher EoE concordance rate compared with non-twin siblings, providing strong evidence for a profound impact of early-life exposures in addition to known genetic underpinnings for susceptibility to EoE⁴⁶. Importantly, CEGIR Investigators Drs. [name] and [name] have provided provocative data about the esophageal microbiome that shows the presence of both overlapping and distinct microbial patterns from that seen in the oral and nasal mucosa⁴⁷. When combined, these pieces of evidence suggest that there may be specific gene-environment interactions in the pathoetiology of EoE, EG, and/or EC. This proposed Pilot/Demonstration Clinical Research Project will explore microbiome profiles in the rare diseases EoE, EG, and EC in order to further characterize disease etiology and progression.

It is feasible to measure the esophageal microbiome. Previous work from CEGIR Investigators Drs. [name] and [name] employed 16S ribosomal RNA gene sequencing to describe the microbiome of normal esophageal mucosal biopsies⁴⁷. These data were originally produced to provide proof of concept for the applicability of the esophageal string test (EST) and are presented here for further proof of feasibility of successfully completing this pilot proposal. Furthermore, differences in the microbiome in health and disease can be identified. [name] et al. observed a significant enrichment of *Streptococcus* species in the healthy esophagus; in contrast, an assessment of the microbiome in untreated EoE subjects demonstrated a shift toward *Haemophilus* species. *Haemophilus* was significantly increased in untreated patients with EoE (n = 11; P = 0.047) compared to controls (n = 25)⁴⁸; no significant differences were observed between controls and treated patients with EoE (steroids and/or diet; n = 26;). Of note, 45% of patients with EoE and control subjects were treated with PPI therapy in an attempt to insure patient homogeneity, eliminate the influence of PPI-responsive esophageal eosinophilia, and control for the potential effect of PPI on the microbiome.

5.8 Rationale

We hypothesize that the GI tissue, serum and/or stool from EoE, EG, and EC subjects will have a distinct dysbiotic microbial pattern as compared with the GI tissue, serum and stool from healthy control subjects. We further hypothesize that EoE, EG, and EC will have both similar and unique patterns of dysbiosis from one another. Due to the similarity of the inflammatory composition in EoE, EG, and EC, dysbiosis in these diseases may follow a common mechanism. However, important and identifiable differences in the local mucosal environments between these diseases are likely to affect the resident microbial taxonomic composition. Understanding both the commonalities and disparities between the esophageal (neutral pH, squamous mucosa), gastric (acidic pH, enzymes, gastric mucosa), and colonic (neutral pH, high baseline bacterial load) dysbiosis will significantly advance our understanding and treatment of EoE, EG, and EC. Furthermore, an understanding of the microbiome may form the foundation for future intervention trials based on antibiotics, probiotics, and/or elemental formulas.

5.9 Primary Objective

We propose a study to quantitatively characterize the microbiome of subjects with EoE, EC, and EG by characterizing alpha and beta diversity at the taxonomic level within and between these groups. We will test the central hypothesis that there will be measurable microbiome differences between these three diseases, which will distinguish each disease from the others and from their disease-specific controls. Following microbiome analysis, a subtractive taxonomic analysis will be performed in order to evaluate and compare dysbiotic mechanisms in EoE vs. EG vs. EC.

5.11 Study Endpoints

5.11.1 Primary Endpoint

Identify significant differences in bacterial genera between EoE, EG and EC and their respective controls in both mucosal biopsies, serum and stool.

5.11.2 Secondary Endpoints

Identify different microbiome or specific bacterial patterns in EoE vs, EG, vs EC in both mucosal biopsies, serum and stool.

5.11.3 Exploratory Endpoints

Determine the impact of PPI treatment on the microbiota in non-inflamed controls and inflamed groups in comparison to the non-PPI treated subjects.

Compare the microbiome in each group between the different geographical locations.
Compare the mucosal biopsy to the stool microbiome in each group and determine if specific IgA and IgG coated bacteria are identified in the stool samples.

5.12 Laboratory Evaluations

5.12.1 Clinical and Research Laboratory Evaluations and Specimen Collection

Pediatric and adult subjects aged ≥ 3 years with upcoming clinical endoscopy will be asked to donate two biopsies, serum and a stool sample for this research. The research biopsies will be used for microbial 16S sequencing, culture, future RNA seq and staining. The serum will be used for future identification of peripheral biomarkers, including total Ig levels, as well as Ig recognizing specific bacteria identified in EGIDs. The stool sample will be used for 16S sequencing and microbiome identification. The samples for blood (5ml), stool, and biopsy will be collected in addition to those in the main study in those patients who consent to sample collection.

6 Potential Risks and Benefits

6.1.2 Potential Benefits

Although there are no direct benefits to participating in this study, it is likely that participation will advance the understanding of these poorly understood diseases. Patients with EoE, EG and EC suffer from a variety of life-impairing problems including difficulty feeding, failure to thrive, vomiting, epigastric or chest pain, dysphagia, food impaction, diarrhea and bloody stools^{2, 53-56}. A better understanding of EoE, EG or EC should help in the formulation of a rational approach to diagnosis and therapeutic intervention and, hopefully, lead to a decrease in the morbidity and mortality associated with these rare diseases.

7 Research Use of Stored Human Samples, Specimens or Data

7.1 Use of Stored Samples/Data

If an endoscopy is to be scheduled, the endoscopic score will be assigned at the time of the procedure. If the endoscopy has been already completed, the score will be performed on the recorded video/pictures.

Archived tissue (biopsy slides) will be evaluated by immunohistochemical staining as described previously.

7.2 Disposition of Stored Samples/Data

The Data Management and Coordinating Center (DMCC) is being used for the storage and management of data for this study. Research samples will be stored at Cincinnati Children's Hospital Medical Center, Colorado Children's Hospital, and the Data Management and Coordinating Center.

8 Study Schedule

8.1 Screening

Subjects enrolled will have a confirmed diagnosis of EoE, EG or EC regardless of their treatment status as we are interested in the relationship between mucosal inflammation, whether currently present or not, with the COMs. Patients who are recruited will either have an established diagnosis of EoE, EG or EC and are undergoing SOC endoscopic analysis at the point of entry or will be patients who are undergoing endoscopy to establish a new diagnosis of EoE, EG or EC. *If EoE, EG, or EC diagnosis is new, enrollment and COM completion will occur within 4 weeks of the diagnostic endoscopy and prior to any treatments for their disease so that the impact of treatments will not impact any of the COMs.*

8.2 Enrollment/Baseline

Investigators and research assistants (RAs) will recruit subjects within their clinical programs, using flyers at the hospital and in outpatient settings, on their respective websites, at academic meetings, and on clinicaltrials.gov. We will notify our academic partners, the American Academy of Allergy, Asthma, and Immunology (AAAAI); the North American Society for Pediatric Gastroenterology Hepatology and Nutrition (NASPGHAN); the American Gastroenterology Association (AGA); and the International Eosinophil Society (IES) about this study so that a recruitment link can be advertised on their respective websites.

Three groups of patients will be recruited: 1) patients with an established diagnosis of EoE, EG or EC 2) patients who are undergoing endoscopy to establish a new diagnosis of EoE, EG or EC 3) Non EoE for controls that are having endoscopy and/or colonoscopy (this group is for the mechanistic microbiome study).. Diagnosis of EoE is based on published criteria, as described earlier in section 5.1. EG will be defined as consistent symptoms and >30 eos /HPF in 5 HPFs^{21, 23}, (25) (23), and EC will be defined as consistent symptoms and >64 eos/HPF²¹; (23); in each case alternative causes of mucosal eosinophilia need to be ruled out. Inclusion and exclusion criteria and rationale are listed in Table 2.

Once enrolled, the new diagnosis cohort of subjects becomes, by definition, part of a longitudinal cohort. Recruited patients will 1.) sign informed consent, 2.) undergo standard of care (SOC) evaluation to capture defined clinical data, 3.) complete PRO questionnaires, and 4.) if not completed, undergo SOC endoscopy and analysis of their esophageal, gastric, or colonic biopsy to measure peak eosinophil count and associated features. Please see section 4.2.1 for a description of the COMs.

8.3 Active Phase (Phase 1)

Subjects receive a complete SOC clinical evaluation that includes: 1) full history of symptoms, atopy, age, gender, 2) family, social and past medical history, 3) history and physical examination, 4) Upper and/or lower endoscopy with biopsy, 5) labs, 6) evaluation of biopsy specimens to determine the number of eosinophils per hpf at 400x light microscopy in the most intensely inflamed hpf (EoE and EC) or in the 5 most intensely inflamed hpf (EG) by the local pathologist. FFPE biopsy specimens obtained as part of SOC will be subsequently verified by the central review pathologists. Each of these will be recorded on standardized histology evaluation forms (included with submission) by the research assistant and logged into the central database. For those subjects who consent to donate research biopsies and blood, these will be collected at each standard of care endoscopy. For those subjects who consent to saliva collection, these samples will be obtained one time only at one of the standard of care endoscopies.

8.4 Follow-up (Phase 2)

In Phase 2 of this study, subjects enrolled in Phase 1 will continue to be followed and assessed at each of the following time points: 1.) annually, 2.) at the time of any change in SOC treatment and 3.) at the time of any endoscopic procedure (up to 4 endoscopies in one year). In scenarios 1, or 2, only PRO and QoL COMs will be completed and in scenario 3, all COMs and histological analysis will be analyzed. All patients will be undergoing SOC treatment during this time; SOC treatment will be the choice of the attending physician and may include systemic or topical steroids, diet, or immunosuppression. This is not an interventional study and thus *treatment will be monitored, but not prescribed* as a part of this protocol. We have taken this approach for several reasons including the capture of “real world” data such that study findings are broadly applicable to the EoE, EG, and EC populations at large, to allow entry of the largest cohort of subjects independent of therapeutic intervention, and to better understand patient adherence to a prescribed therapeutic regimen as it relates to disease course.

8.5 Early Termination Visit

If a subject withdraws from the study, we will assess their symptoms on the current treatment during their clinic visit.

9 Assessment of Safety

This is not an interventional study. As such, monitoring of AEs will be limited to those developing within 3 days after the research biopsies are collected (for those subjects who consent to the additional biopsies).

9.1 Adverse Event (AE)

This section defines the types of AEs and outlines the procedures for appropriately collecting, grading, recording, and reporting them. Adverse events that are classified as serious according to the definition of health authorities must be reported promptly to the sponsor. Information in this section complies with International Conference on Harmonization (ICH) Guideline E2A: *Clinical Safety Data Management: Definitions and Standards for Expedited Reporting* and ICH Guideline E6: *Guideline for Good Clinical Practice*, and applies the standards set forth in the National Cancer Institute Common Terminology Criteria for Adverse Events (NCI-CTCAE) (version 4.03 2010-06-14). These criteria have been reviewed by the study investigators and the sponsor and have been determined appropriate for this study population.

Reportable AEs for this observational study will be limited to those related to the additional biopsy's. The worsening of a participant's pre-existing medical condition will not be considered an AE unless

the worsening is related to the additional biopsy procedure. Reportable AEs will include, but are not limited to, the following:

Collection of additional biopsies at Endoscopy - Adverse events associated with the collection of additional biopsies include bleeding, infection and perforation. Each of these would be categorized as being significant enough to require a visit to a clinician to evaluate association with laboratory or testing abnormalities.

9.2 Serious Adverse Event (SAE)

Reportable SAEs for this observational study will be limited to those related to additional endoscopy biopsies. A Serious Adverse Event (SAE) is defined as an AE meeting one of the following conditions:

- Death during the period of protocol-defined surveillance
- Life Threatening Event (defined as an event that places a participant at immediate risk of death)
- Inpatient hospitalization or prolongation of existing hospitalization during the period of protocol-defined surveillance
- Congenital anomaly or birth defect
- Persistent or significant disability/incapacity
- Any other condition that, in the judgment of the investigator, represents a significant hazard, such as an important medical event that does not result in one of the above outcomes, may be considered an SAE when the event is related to the additional endoscopy biopsy and jeopardizes the participant or requires medical or surgical intervention to prevent one of the outcomes listed above.

9.3 Methods and Timing for Assessing, Recording, and Analyzing Adverse Events

9.3.1 Methods and Timing for Assessment

Subjects who consent to collection of additional research biopsies during a SOC endoscopy procedure will have their electronic medical record accessed within 3 days after the procedure to evaluate whether the patient had any difficulties reported.

AE/SAE Grading and Relationship Assignment

Intensity (severity) Scale

Each AE, will be assessed using NCI-CTCAE grading criteria for severity and classified into one the categories below:

- **Grade 1 (Mild):** Asymptomatic or mild symptoms; clinical or diagnostic observations only; intervention not indicated. Event requires minimal or no treatment and does not interfere with the participant's daily activities.
- **Grade 2 (Moderate):** minimal, local or noninvasive intervention indicated; limiting age-appropriate instrumental Activities of Daily Living (ADL)*. Event results in a low level of inconvenience or concern with the therapeutic measures. Moderate events may cause some interference with functioning.

- **Grade 3 (Severe):** Severe or medically significant but not immediately life-threatening; hospitalization or prolongation of hospitalization indicated; disabling; limiting self care ADL**. Event interrupts a subject's usual daily activity or functioning and may require systemic drug therapy or other treatment. Severe events are usually incapacitating.
- **Grade 4 (Life threatening):** Urgent intervention indicated. Any adverse drug experience that places the participant, in the view of the investigator, at immediate risk of death from the event as it occurred.
- **Grade 5 (Death):** Death related to AE.

*Instrumental ADL refer to preparing meals, shopping for groceries or clothes, using the telephone, managing money, etc.

**Self care ADL refer to bathing, dressing and undressing, feeding self, using the toilet, taking medications, and not bedridden.

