5.3 Clinical Evaluations

Subjects will be evaluated using the COMs as described in section 4.2.1. No additional clinic visits will be needed outside of standard-of-care.

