9.3.1.2 Recording/Documentation

All reportable adverse events that are identified will be recorded on an appropriate case report form (CRF). AEs developing within 3 days after the SOC endoscopy in subjects who consented to collection of extra research biopsies during SOC endoscopy procedure will be considered. All reported adverse events will be classified using the Common Terminology Criteria for Adverse Events (CTCAE) developed and maintained by CTEP at National Cancer Institute.

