9.4.1 NIAID Medical Monitor Review

Upon entry of a serious adverse event, the DMCC created Adverse Event Data Management System (AEDAMS) will immediately notify the, site PIs, the NIAID Medical Officer (MO), of any reported adverse events via email.

Serious adverse events will be reviewed by The NIAID Medical Officer (MO) within 2 business days after notification by the DMCC via AEDAMS. A back-up notification system is in place so that any delays in review by the MO beyond a specified period of time are forwarded to a secondary reviewer. Cumulative reports of AEs and SAEs will be reviewed at a minimum of every 6 to 12 months.

Non-serious expected adverse events: Except those listed above as immediately reportable, non-serious expected adverse events that are reported to or observed by the investigator or a member of his/her research team will be submitted to the DMCC in a timely fashion (within 20 working days).

The DMCC will post aggregate reports of all reported adverse events for review by NIAID Medical Officer and Project Manager

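### The chart check for biopsy adverse events may be made before the 3-day reportable window closes, so a compliant site can leave part of the window unreviewed

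*Protocol*

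**What the plan says.** Three places in the Protocol fix the period and the method.

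- **Window for monitoring.** The opening of Section 9 says that "monitoring of AEs will be limited to those developing within 3 days after the research biopsies are collected".
- **Window for recording.** Section 9.3.1.2 says that "AEs developing within 3 days after the SOC endoscopy in subjects who consented to collection of extra research biopsies" will be considered.
- **Method of finding events.** Under Section 9.3.1, participants who agree to extra research biopsies "will have their electronic medical record accessed within 3 days after the procedure to evaluate whether the patient had any difficulties reported".

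Section 9.1 names what the window is meant to catch: "Adverse events associated with the collection of additional biopsies include bleeding, infection and perforation". It treats each as an event that would bring the participant to a clinician.

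The other route to detection is passive. Section 9.4.1 requires submission of "non-serious expected adverse events that are reported to or observed by the investigator or a member of his/her research team", and the reporting clocks in Section 9.4.3 start when the investigator or site learns of an event. No study visit serves as a second look: Section 5.3 states that "No additional clinic visits will be needed outside of standard-of-care", and the schedule in Appendix B has no row for adverse event assessment.

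**The concern.** The reportable window and the deadline for the check are the same 3 days. The window closes at the end of day 3, and the check must be done by then and may be done sooner. A site that opens the chart on the day of the procedure or the day after has met Section 9.3.1 in full and need not look again, although the window in Sections 9 and 9.3.1.2 is still open.

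Events related to the extra biopsies are the only safety outcome of the study (Sections 9 to 9.2). The extra biopsies are a risk that the study itself adds. They are offered to participants from age 3 and taken at each standard-of-care endoscopy (Sections 5.4.1 and 8.3), with up to four endoscopies in a year (Section 8.4). Section 9.3.3 makes the medical monitor's review the primary analysis of adverse events, and Section 9.4 leaves oversight to the principal investigator and that monitor. Both see only what has been found. When few events are expected, a count at or near zero is hard to interpret if the search may have stopped before the period ended.

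**Working it through.** There is no sample size, power or significance level here and no stated figure to reproduce. The check compares time limits.

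**Inputs**

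| Item | Value | Source |
|---|---|---|
| Window for monitoring | 3 days after the research biopsies | Section 9, opening |
| Window for recording | 3 days after the endoscopy | Section 9.3.1.2 |
| Latest time of the record check | day 3 after the procedure | Section 9.3.1 |
| Earliest time of the record check | none stated | Section 9.3.1 |
| Repeat check or coverage requirement | none stated | Section 9.3.1 |
| Study visits or scheduled AE contacts after the biopsy | none | Section 5.3, Appendix B |

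**Step 1: time left unreviewed.** If the only check is made t days after the procedure, with t anywhere from 0 to 3, the unreviewed share of the window is (3 − t)/3.

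| Time of check | Days unreviewed | Share of window |
|---|---|---|
| day 0 (t = 0) | 3 of 3 | 3/3 = 100% |
| day 1 (t = 1) | 2 of 3 | 2/3 = 67% |
| day 2 (t = 2) | 1 of 3 | 1/3 = 33% |
| end of day 3 (t = 3) | 0 of 3 | 0/3 = 0% |

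Every row complies with Section 9.3.1. These are shares of time, not of events. The Protocol gives no rates and no timing for these events, so they cannot be converted into a number missed.

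**Step 2: delay in charting.** For an event to be visible, it must arise, bring the participant to a clinician and be entered in the record. If that takes d days, a check at time t sees only events that arose by t − d. With t = 3, events from the last d days of the window are still missed. The Protocol gives no value for d. For any d above zero, the latest permitted check also falls short of full coverage.

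**Step 3: what remains afterwards.** After the check, an in-window event reaches the study only if someone reports it to the team or the team comes across it (Sections 9.4.1 and 9.4.3). Those sections say how to handle events already known. They do not call for a search.

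**Step 4: effect of the change.** A review made after day 3 has ended and covering the whole interval leaves 0 of 3 days unreviewed. The present wording leaves anything from 0 to 3. Events charted after that review could still be missed.

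**The case against.** Several points on the other side have force.

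- **Passive reporting stays open.** Section 9.3.1.2 puts no condition on when an event is discovered, and the clocks in Section 9.4.3 run from awareness. An in-window event learned of long after the check is still reportable. A reader might infer that events after an early check are never picked up. The documents do not support that: such events are not actively sought, but they can still be reported. Investigators recruit within their own clinical programs (Section 8.2), and events needing a clinician may well reach them, though nothing guarantees it.
- **Nothing requires an early check.** One made at the end of day 3 also complies, and Section 9.3.1 neither says that the record is opened only once nor forbids another look. A reader might infer a systematic under-count. The text shows only that under-counting is possible.
- **A kinder reading exists.** The 3 days could be meant as the period reviewed. As written, however, they attach to when the record is accessed, and many sites must apply the sentence as it stands.
- **Event shares are tempting.** If event times and check times were independent and uniform over the 3 days, the chance that an event follows the check would be 1 − 1.5/3 = 0.5; with a check fixed at day 1 it would be (3 − 1)/3 = 0.67. The Protocol supports neither assumption. The share missed by active review could be anywhere from none to all, so these figures should not be used as estimates.
- **The stakes are limited.** Section 9.3.3 expects few events, Section 9.4 classes the study as low risk, and no scientific analysis uses the adverse event data.
- **The Manual of Operations may set the timing.** It is not available here. Even if it does, the Protocol sentence would still permit an early check.

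The first, second and fifth points stand and limit the claim. None of them removes the mismatch between the check and its window.

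**Conclusion.** The concern holds in a limited form. The one active method of finding biopsy adverse events has a deadline equal to the end of the window it serves, with no earliest time and no coverage requirement. A fully compliant check can leave 0 to 3 days of the 3-day window unreviewed, and the latest permitted check can still miss events not yet charted. This conclusion rests on reading Section 9.3.1 literally and on the absence of any other active follow-up in the Protocol.

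The wording permits under-counting of the study's only safety outcome. It does not force it, and the number of events affected cannot be estimated from the Protocol. The Aim 1 and Aim 2 analyses are untouched. It is a worthwhile correction to safety ascertainment and does not threaten the study's main conclusions.

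**What to change.** Reconcile the opening of Section 9, Section 9.3.1 and Section 9.3.1.2. Leave the 3-day reportable window as it is and change the sentence in Section 9.3.1. Suggested wording: *For participants who have research biopsies taken, the electronic medical record will be reviewed after the third day following the procedure has ended. The review will cover the whole period from the procedure to the end of that day, including later entries that describe an onset within it. An earlier look at the record may be made in addition.*

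The cost is small. If the sponsor keeps an early look and adds the closing review, each biopsy procedure needs a second brief chart look. If the single check is simply moved later, the number of checks is unchanged, but an event found only by chart review, including a serious one, would be discovered slightly later. Because the clocks in Section 9.4.3 run from awareness, its report would move back too. Keeping the early look avoids that delay for events already charted by then. No additional visit is needed, and the timelines for spontaneously reported events do not change.
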